### 4.3. Treatment Compliance

Treatment compliance will be derived based on the information from the study drug administration eCRF page.

Treatment compliance will be calculated as follows:

Treatment compliance (%) =  $100 \times [\text{number of doses taken} / \text{total treatment duration in weeks rounded up to nearest integer}]$

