4. STUDY DESIGN

4.1. Overall Design

This is a randomized, double-blind, placebo-controlled, parallel-group, 4-arm, multicenter study in severely obese subjects with T2DM. Subjects who are ≥ 18 and ≤ 70 years of age and have a BMI ≥ 35 kg/m² to ≤ 50 kg/m² are eligible to participate if they have a HbA_{1c} of $\geq 6.5\%$ to $\leq 9.5\%$ at the screening visit on diet and exercise alone or on a stable dose of single oral AHA or dual-combination oral AHAs for ≥ 12 weeks prior to screening. A target of 188 subjects will be randomly assigned in this study.

Subjects meeting all enrollment criteria will enter a 2-week run-in phase, which is to occur approximately 1 week after the screening visit and is designed to train the subject on SC self-injection and to establish the subject's ability to comply with the protocol-specified requirements. On Day 1, subjects who continue to meet eligibility criteria, will be randomly assigned in a 1:1:1:1 ratio to blinded treatment with placebo or JNJ-64565111 5.0 mg, 7.4 mg, or 10 mg and enter a 12-week treatment phase. Post-randomization visits will be conducted at Week 2, 6, 12/end-of-treatment [EOT] visit, and the SAE follow-up visit 5 weeks after the last dose of study drug. At Weeks 4 and 10, all subjects will be contacted preferably by telephone to reinforce the adherence to diet and exercise, study drug dosing reminder, assessment of subjects' status, and compliance with the protocol procedures (eg, diary completion reminder).

During the pretreatment/run-in and treatment phases, subjects will undergo efficacy and safety assessments including physical examination, ECG, laboratory testing and vital signs measurement. A serum pregnancy test will be performed at screening and Week 12/EOT along with a urine pregnancy test at Day 1 in women of childbearing potential.

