On Day 1, subjects randomly assigned to the double-blind treatment arms will receive a supply of their randomly-assigned study drug and will be reminded of the once weekly dosing regimen and to record the date and time of each administered dose in the study drug diary. Subjects will self-administer the first dose of JNJ-64565111 or matching placebo at the site under the supervision of study staff.

Drug Administration

Subjects will be instructed to administer study drug SC once weekly for the entire duration of the 12-week treatment phase or until early discontinuation.

Subjects will be instructed to inject to the 4 quadrants of the anterior abdominal wall. For consistency, and to avoid dosing in the same abdominal area, subjects should be instructed to begin in one quadrant and on subsequent dosing days proceed in the next quadrant in a counterclockwise manner.

Injections can be done at any time of day irrespective of meals. However, it is preferable that study drug be injected during the same overall time period of the day on a week-to-week basis.

Study drug should be taken on the same day of the week throughout the study (ie, the regularly scheduled study drug day).

[figure not shown]
If the day of the once weekly injection coincides with the day of a clinic visit, subjects are NOT to inject JNJ-64565111 or matching placebo before arriving at the clinic. Instead, AFTER all study visit procedures have been completed, subjects may self-administer blinded study drug either at the study site or once they have returned home.

Subjects are to record the date and time of study drug administration on the study drug diary, and should mark a calendar to remind them of when to take the next weekly dose. Subjects will be instructed to record the date and time of each self-injection throughout the run-in and treatment phase which allows an assessment of treatment compliance and the relationship of PK measurements and safety assessments to the time of study-drug dosing. The information will be entered into eCRFs by the site personnel.

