Subjects should be instructed not to take 2 doses within 3 days (72 hours) of each other. If a subject misses taking the next dose of study drug on their regularly scheduled study drug day, the missed dose should be taken as soon as possible, if there are at least 3 days (72 hours) until their next regularly scheduled study drug day. If there are less than 3 days remaining, the subject should skip the missed dose and take the next dose on their regularly scheduled study drug day.

Study-site personnel will instruct subjects on how to store study drug for at-home use as indicated for this protocol. Figure 3 is a schematic diagram of the study drug injection schedule.

Figure 3: Schematic Diagram of Drug Injection Schedule

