**AMENDMENT HISTORY**

SECTION(S)	CHANGE and RATIONALE
Global Change	“Pulse Pressure Product” and “Rate Pressure Product” were used interchangeably; the term “Rate Pressure Product” will be used going forward.
Abbreviations	Added abbreviation of ANCOVA, AHA and ATC. Remove abbreviations that are not in the body of the text. Minor corrections were made for AE(s), PRO, and PROMIS SF 10a.
1	Change the Clinical Protocol JNJ-64565111OBE2002 date to 5 April 2018.
2.1	Visit windows now include post-Week 12 to account for subjects brought back for visits to reduce Lost To Follow Ups.
2.2	Remove Section 2.2 Pooling Algorithm for Analysis Centers
2.2.2	Refined mITT Analysis Set definition to include subjects taking at least one dose of study medication.
2.2.2	Clarify that the Completers’ Analysis Set is defined by the Treatment Disposition eCRF status.
2.3	Remove Region because this study is conducted in the US only. Remove Ethnicity, Baseline fasting HOMA-B, and Baseline eGFR to reduce the number of subgroup analyses. A minor correction for the baseline HbA 1c categories was made.
2.3, 4.1	Correct variable name for HOMA-B and HOMA-IR.
4.1	Demographics tables will be generated for 5 analysis sets: ITT, mITT, Safety, PK, and Completers. Added variables rate pressure product (bpm*mmHg), Beta-hydroxybutyrate (mmol/L). Removed ratios of LDL-C/LDL-C. Added unit (%) for HbA 1c . A minor correction for baseline HbA 1c categories was made.
4.2	Screen failures will not be summarized. Protocol deviations will be listed that may include deviations related to medication dispensed. Removed the bullet of “reasons for discontinuation from study” as it is redundant with the paragraph below.
4.3	Treatment compliance formula was refined to only account for period of time between first and last dose; non-compliance is not counted after the last dose.
4.2, 4.3	Changed “study agent” to “treatment” to keep the consistency through the SAP.
4.4	For the purpose of summarizing exposure, treatment duration does not take drug interruptions into account. Steps for imputing missing treatment end dates were refined. Removed “study agent” from the second paragraph of the section. Replaced “treatment duration prior to rescue medication” and “treatment duration” for “treatment duration” and “overall duration”, respectively.
4.5	Protocol deviations, as identified by the Study Team, will be listed but not summarized.

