## 1. INTRODUCTION

This statistical analysis plan (SAP) contains the definitions of analysis sets, key derived variables, and statistical methods for the analyses of efficacy and safety data from study JNJ-64565111OBE2002. This SAP is based on the Clinical Protocol JNJ-64565111OBE2002 dated 5 April 2018. Titles, mock-ups and programming instructions for all statistical outputs (tables, figures and listings) will be provided in a separate document entitled Data Presentation Specifications (DPS). A separate Data Monitoring Committee (DMC) SAP will describe the data analysis for DMC reviews.

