### 4.4. Extent of Exposure

Treatment duration will be calculated (in days) based on the dosing schedule as follows:

Date of last dose – date of first dose + 8 days

If the end date of the study medication intake is not known (e.g., subject is lost to follow-up), it will be imputed as the earlier of: (1) the date of death, (2) the disposition date (i.e., end of study date, end of treatment date), or (3) 28 days from the date that the last medication kit was dispensed.

Descriptive statistics (N, mean, standard deviation, median, and range) will be presented by treatment group for treatment duration prior to rescue medication (excluding the duration after initiation of rescue medications), and the overall treatment duration (including after initiation of rescue medication) for the safety analysis set.

The number and percentage of subjects who receive treatment will also be summarized by treatment group with the duration in each of the following categories:

- For the entire double-blind treatment phase, <2 weeks, 2 to <6 weeks, 6 to <10 weeks, and  $\geq 10$  weeks

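### Under the SAP's only duration formula, a subject who injects exactly once a week cannot reach 100% compliance: 12 on-schedule doses score 92.3%

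*SAP*

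**What the plan says.** SAP 4.3 derives compliance from the study drug administration eCRF page, as 100 times the "number of doses taken" divided by the "total treatment duration in weeks rounded up to nearest integer". It gives no start date, end date or added days, and does not refer to another section.

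SAP 4.4, which follows directly under Extent of Exposure, calculates treatment duration in days as "Date of last dose – date of first dose + 8 days". It adds a rule for imputing an unknown end date and speaks of an overall treatment duration. It does not say that this is the denominator for 4.3. No other duration formula appears in the SAP, and Protocol 6.4 (Study Drug Compliance) gives none.

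On dosing, Protocol 6.1 says: "Subjects will be instructed to administer study drug SC once weekly for the entire duration of the 12-week treatment phase". Study drug is to be taken on the same day each week. The one spacing limit is: "Subjects should be instructed not to take 2 doses within 3 days (72 hours) of each other".

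SAP 1 places "Titles, mock-ups and programming instructions for all statistical outputs" in a separate document, the Data Presentation Specifications.

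**The concern.** A compliance percentage should equal 100% when every scheduled dose is taken on schedule. A programmer who meets an undefined total treatment duration in 4.3 will naturally use the one formula the SAP offers, in the next section. A weekly dose accounts for 7 days, so n doses account for 7n days. The 4.4 formula gives 7n + 1 days, and rounding up turns the extra day into a whole week without a dose.

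Two distortions follow. The shortfall depends on how long the subject was treated, so an arm with more early stopping shows lower mean compliance even if nobody missed a dose while on treatment. In addition, a slightly early last dose scores better than a punctual one. The compliance summary could then be read as a difference in adherence between arms when it reflects discontinuation.

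**Working it through.** The documents state no compliance figure, so there is nothing to reproduce first.

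**Inputs.** Numerator and rounding rule: SAP 4.3. Duration: SAP 4.4. Weekly dosing: Protocol 6.1. Twelve planned doses is an inference, because the dosing diagram is not shown. Protocol 4.1 has the "SAE follow-up visit 5 weeks after the last dose of study drug" and also gives the post-treatment phase as 4 weeks. The last planned dose therefore falls one week before Week 12. With Week 12 at Day 85 (SAP Table 2.1.1), that is Day 78, and doses fall on Days 1, 8, …, 78.

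**General result.** For n on-schedule weekly doses:
- last − first = 7(n − 1) days
- 4.4 duration = 7(n − 1) + 8 = 7n + 1 days
- weeks = n + 1/7, rounded up to n + 1
- compliance = 100 × n/(n + 1)

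| Doses, all on schedule | Last − first (days) | + 8 (days) | Weeks | Rounded up | Compliance |
|---|---|---|---|---|---|
| 1 | 0 | 8 | 1.14 | 2 | 50.0% |
| 2 | 7 | 15 | 2.14 | 3 | 66.7% |
| 4 | 21 | 29 | 4.14 | 5 | 80.0% |
| 6 | 35 | 43 | 6.14 | 7 | 85.7% |
| 12 | 77 | 85 | 12.14 | 13 | 92.3% |

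**Timing of the 12th dose.**
- 1 to 4 days early: last − first is 76 to 73 days; + 8 gives 84 to 81 days; 12 weeks after rounding up; 12/12 = 100%.
- On time: 85 days; 13 weeks; 12/13 = 92.3%.
- 1 to 4 days late: 86 to 89 days; 13 weeks; 92.3%.

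A 12th dose 4 days early falls 3 days after the 11th, which is at the protocol's 72-hour limit, so such timings can occur.

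**One missed mid-course dose, last dose on time.** 11/13 = 84.6%.

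**Effect on an arm's mean (assumed mixes, for illustration only).** Suppose a fraction p of an arm stops after 4 on-schedule doses and the rest take all 12 on schedule. Mean compliance is (1 − p) × 92.3% + p × 80.0%: 92.3% for p = 0, 91.1% for p = 0.1, 89.8% for p = 0.2 and 88.6% for p = 0.3. Nobody missed a dose in any of these cases.

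**Check of the proposed denominator,** (last − first + 7)/7 rounded to the nearest week:
- n on-schedule doses: 7n/7 = n, so 100% for every n.
- 12 doses, last dose 3 days early: 81/7 = 11.57, rounds to 12, 100%.
- 12 doses, last dose 3 days late: 87/7 = 12.43, rounds to 12, 100%.
- 12 doses, last dose 4 days early: 80/7 = 11.43, rounds to 11, 109.1%.
- 12 doses, last dose 4 days late: 88/7 = 12.57, rounds to 13, 92.3%.
- One missed mid-course dose: 11/12 = 91.7%.
- One additional dose within the same 77 days: 13/12 = 108.3%.

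**The case against.** The strongest objection is that the gap may already be closed. The SAP sends programming instructions to the Data Presentation Specifications, and programmers would work from that document. This stands: the point can be made about the SAP text but not about what was programmed.

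Second, nothing inferential depends on the figure. The analysis sets in SAP 2.2 and the models in SAP 5 do not use it, 4.3 sets no threshold, and the PK exclusions in SAP 7.1 have their own dosing-deviation criteria. This also stands. A reader might infer that efficacy or dose-response results are affected, but the documents give no support for that.

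Third, a reader might go further and say that 4.3 leaves three denominators open, with 12 perfect doses scoring 92.3% (4.4), 100% (last − first + 1 = 78 days, rounded up to 12 weeks) or 109.1% (last − first = 77 days, 11 weeks). The documents do not support that. The second and third versions have no wording behind them in the body of the SAP. They rest only on the amendment history: "Treatment compliance formula was refined to only account for period of time between first and last dose". A change log that differs from the current text is not an error; here it is at most a sign of intent. The plain difference is also implausible. It divides by zero for a single dose and departs from the SAP's day-counting convention in 2.4, which adds 1 and has no Day 0.

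Fourth, one could say that 4.4 applies by default, so there is no ambiguity. That may be so, but it does not help: applying 4.4 is what produces n/(n + 1).

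**Conclusion.** The point holds and is minor. Followed as written, SAP 4.3 and 4.4 together give a compliance figure that cannot reach 100% for exact weekly dosing. It understates adherence by 7.7 percentage points for 12 doses (100 − 92.3), 20 points for 4 and 50 points for 1. It also ranks a slightly early last dose above a punctual one.

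This rests on one assumption: that the 4.4 duration is the one meant in 4.3, which 4.3 does not say. If it is not meant, 4.3 has no stated denominator and the same fix is needed. The count of 12 doses is inferred, but n/(n + 1) holds for any number of doses. The arithmetic is exact. The effect is confined to a descriptive compliance summary, and the unseen specifications may already handle it. The + 8 days is not challenged as an exposure measure.

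**What to change.** In SAP 4.3:
- State the denominator as (date of last dose − date of first dose + 7)/7, rounded to the nearest week, and state that the + 8 days exposure duration of 4.4 is not used for compliance.
- Keep the 4.4 imputation rule for subjects whose last-dose date is unknown, so that their denominator stays defined.
- Report values above 100% uncapped and without attributing them to early dosing. Additional doses also produce them, and a cap would hide those.

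Leave 4.4 unchanged for exposure. If the Data Presentation Specifications already define a denominator under which on-schedule dosing scores 100%, copying it into 4.3 is enough.

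Rounding to the nearest week matters. With + 7 days and rounding up, a last dose 1 day late would give 85 days, 13 weeks and 92.3%.

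The cost is a few sentences in 4.3 and one line of code, with no effect on any other analysis. The small downside is that a last dose 4 or more days off schedule shifts the denominator by one week, as shown in the check above.

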### 4.4. Extent of Exposure

Treatment duration will be calculated (in days) based on the dosing schedule as follows:

Date of last dose – date of first dose + 8 days

If the end date of the study medication intake is not known (e.g., subject is lost to follow-up), it will be imputed as the earlier of: (1) the date of death, (2) the disposition date (i.e., end of study date, end of treatment date), or (3) 28 days from the date that the last medication kit was dispensed.

Descriptive statistics (N, mean, standard deviation, median, and range) will be presented by treatment group for treatment duration prior to rescue medication (excluding the duration after initiation of rescue medications), and the overall treatment duration (including after initiation of rescue medication) for the safety analysis set.

The number and percentage of subjects who receive treatment will also be summarized by treatment group with the duration in each of the following categories:

- For the entire double-blind treatment phase, <2 weeks, 2 to <6 weeks, 6 to <10 weeks, and  $\geq 10$  weeks

### 4.5. Protocol Deviations

Subjects with major protocol deviations will be identified prior to database lock and provided in a listing.

### 4.6. Prior and Concomitant Medications

Prior and Concomitant medications will be coded using the World Health Organization Drug Dictionary (WHO-DD). Prior medications are defined as any therapy used before the day of first dose (partial or complete) of study agent. Concomitant medications are defined as any therapy used on or after the same day as the first dose of study agent, including those that started before and continue on after the first dose of study agent.

Summaries of concomitant medications will be presented by Anatomical Therapeutic Chemical (ATC) term and treatment group. The proportion of subjects who receive each concomitant

medication will be summarized as well as the proportion of subjects who receive at least one concomitant medication. In addition, concomitant medications of interest will be presented.

Prior medications will be summarized by treatment group/dose level and ATC term.

## **5. EFFICACY**

The primary analysis of the primary, secondary and exploratory efficacy endpoints will be based on the modified intent-to-treat (mITT) analysis set. Only those measurements taken up to the last dose of study drug plus 14 days will be included in the analysis. A secondary analysis of the primary and secondary efficacy endpoints will be based on the intent-to-treat (ITT) analysis set. This analysis will include post-baseline measurements taken within the 12-week double-blind phase regardless of rescue medication initiation, and regardless of whether on or off-treatment. Sensitivity analyses based on the completers' analysis set will also be performed for the primary endpoint.

Efficacy data will be analyzed according to the initial randomization assignment, regardless of the actual treatment received.

### **5.1. Analysis Specifications**

#### **5.1.1. Level of Significance**

The type I error rate will be strongly controlled at  $\alpha=5\%$  for each of the primary endpoint and secondary endpoints. The Hochberg approach will be used to adjust for the multiplicity of the comparisons of each of the JNJ-64565111 doses versus placebo for each of the primary and major secondary efficacy endpoints. Adjusted p-values will be provided.

Unless otherwise specified, all statistical tests will be interpreted at a 2-sided significance level of 5% and all confidence intervals at a 2-sided confidence level of 95%. Nominal p-values will be presented for endpoints other than those described above.

#### **5.1.2. Data Handling Rules**

Unlike other assessments which are scheduled to be collected once at each visit, three consecutive readings of the SBP, DBP and pulse rate will be measured (at intervals of at least 1 minute apart) and recorded. The average of the multiple measurements will be computed at each visit for all subjects and this averaged value will be used in all the analyses and summaries of blood pressure and pulse rate. Details regarding the handling of missing and partial dates, the derivation of Patient-Reported Outcomes (PRO) measures are described in the Data Presentation Specifications (DPS).

### **5.2. Primary Efficacy Endpoint**

#### **5.2.1. Definition**

The primary efficacy endpoint will be the percentage change in body weight from baseline to Week 12.

### 5.2.2. Estimand

**Population:** diabetic, obese subjects in the mITT analysis set who are  $\geq 18$  and  $\leq 70$  years of age, have a BMI  $\geq 35$  to  $\leq 50$  kg/m^2, and have a HbA1c  $\geq 6.5\%$  to  $\leq 9.5\%$ .

**Variable:** percentage change in body weight from baseline to Week 12

**Population-level summary:** mean percentage change in body weight from baseline to Week 12.

### 5.2.3. Analysis Methods

#### Primary Analysis

The primary efficacy endpoint will be analyzed based on the mITT analysis set using a mixed model for repeated measures (MMRM). The analysis will use the observed data through Week 12 while on treatment (up to the last dose of study drug plus 14 days). The analysis model will include the fixed, categorical effects of treatment, visit, and treatment-by-visit interaction, as well as the continuous covariates of baseline body weight and baseline-by-visit interaction. An unstructured covariance will be used to model the within-patient errors. The treatment comparisons will be made between each of the JNJ-64565111 treatment groups and placebo at Week 12 based on this model.

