9.3. Populations for Analyses

For purposes of analysis, the following populations are defined:

Table 5: Subject Population Definitions

Population	Description
Enrolled	All subjects who sign the ICF
ITT analysis set	all subjects who are randomly assigned to a treatment group and have a baseline measurement of body weight
mITT analysis set	all ITT subjects who have at least 1 post-baseline measurement of body weight within 7 days following a dose of study drug and before initiation of any rescue therapy
Completers' analysis set	of all mITT subjects who have completed 12 weeks of double-blind treatment (ie, documented in the eCRF by the investigators that the subject has completed participation in the study through the Week 12 visit) and without initiation of glycemic rescue therapy
Safety analysis set	all randomized subjects who have received at least one dose of study drug

Key: eCRF=electronic case report form; ICF=informed consent form; ITT=intent-to-treat; mITT=modified intent-to-treat.

The primary efficacy analysis, to demonstrate the superiority of JNJ-64565111 compared with placebo on percentage reduction in body weight from baseline to Week 12, as well as all secondary efficacy analyses, will be based on the modified intent-to-treat (mITT) analysis set and will include only those measurements taken up to and including the last dose of study drug plus 7 days and prior to initiation of any glycemic rescue therapy. A secondary analysis of the primary and secondary efficacy endpoints will be based on the intent-to-treat (ITT) analysis set. This analysis will include all measurements. Sensitivity analyses based on the completers' analysis set will also be performed for the primary endpoint.

Efficacy data will be analyzed according to the initial randomization assignment, regardless of the actual treatment received. Safety data will be analyzed according to the predominant treatment received, in the event that a subject receives a treatment other than that to which he/she is randomly assigned.

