9.4. Statistical Analyses

9.4.1. Efficacy Analyses

All hypotheses will be tested 2-sided at a 5% significance level unless otherwise notes.

Primary Efficacy Endpoint

The primary efficacy endpoint will be the percentage change in body weight between JNJ-64565111 and placebo from baseline to Week 12.

The primary efficacy endpoint will be analyzed based on the mITT analysis set using a mixed model for repeated measures (MMRM). The analysis will use the observed data through Week 12 while on treatment (up to the last dose of study drug plus 7 days) and prior to rescue medication. The analysis model will include the fixed, categorical effects of treatment, visit, and treatment-by-visit interaction, as well as the continuous covariates of baseline body weight and baseline-by-visit interaction. An unstructured covariance will be used to model the within-patient errors. The treatment comparisons will be made between each of the JNJ-64565111 treatment groups and placebo at Week 12 based on this model.

A secondary analysis of the primary endpoint will be based on the ITT analysis set and will employ pattern mixture models using multiple imputation methods. This analysis will use all observed data, including the measurements off treatment. Responses for subjects who discontinued from the study earlier than Week 12 will be imputed based on subjects who discontinued treatment prematurely but subsequently provided off-treatment measurements. The imputation will be done within randomized treatment groups. Data will be analyzed using the same model as in the primary analysis. The treatment comparisons between each of the JNJ-64565111 treatment groups and placebo will be made at Week 12. Details of this approach will be provided in the statistical analysis plan (SAP).

Finally, the primary efficacy endpoint will be analyzed based on the completers analysis set. Additional analysis using a Multiple Comparison Procedure – Modeling approach ([Bornkamp 2009](#); [Pinheiro 2014](#)) will be performed to explore the dose-response relationship.

Secondary Efficacy Endpoints

Secondary efficacy analyses at Week 12 will include the absolute change in body weight from baseline and the proportion of subjects with $\geq 5\%$ weight loss.

The absolute change in body weight from baseline at Week 12 will be analyzed with an MMRM model similar to the primary efficacy endpoint based on the mITT analysis set.

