### **2.2.2. Efficacy Analysis Sets**

- The intent-to-treat (ITT) analysis set will include all subjects who are randomly assigned to a treatment group and have a baseline body weight measurement.
- The modified intent-to-treat (mITT) analysis set includes all ITT subjects who have taken at least one dose of study medication and have at least 1 post-baseline body weight measurement.
- The completers' analysis set will consist of all mITT subjects who have completed 12 weeks of treatment (i.e., documented in the Treatment Disposition eCRF by the investigators that the subject has completed treatment through the Week 12 visit window).

The primary efficacy analysis, to demonstrate the superiority of JNJ-64565111 compared to placebo on percentage reduction in body weight from baseline to Week 12, as well as all secondary efficacy analyses, will be based on the mITT analysis set.

A secondary analysis of the primary and secondary efficacy endpoints will be based on the ITT population (including data after initiation of rescue medication and data after the on-treatment period). This analysis will include all measurements through the Week 12 visit window. Supportive analyses based on the completers' analysis set will also be performed for the primary endpoint.

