### **5.3.2. Analysis Methods**

#### **Primary Analysis**

The absolute change in body weight from baseline at Week 12 will be analyzed with an MMRM model similar to the primary efficacy endpoint based on the mITT analysis set.

The proportion of subjects with  $\geq 5\%$  weight loss at Week 12 will be analyzed using the mITT analysis set. Only subjects with observed data at Week 12 while on treatment (up to the last dose of study drug plus 14 days) are eligible to be considered responders ( $\geq 5\%$  weight loss). Subjects without an on treatment weight measurement at Week 12 will be considered non-responders. A logistic regression model including treatment as a fixed effect, and baseline weight as a covariate will be used for the analysis. The odds ratio and adjusted p-value for the treatment comparison between each of the JNJ-64565111 treatment groups versus placebo at Week 12 based on this model will be provided.

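### Does the SAP leave open whether weights recorded after glycemic rescue enter the primary weight analysis?

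*SAP*

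**What the plan says.** **Protocol.** Section 9.3 bases the primary and secondary efficacy analyses on measurements "up to and including the last dose of study drug plus 7 days and prior to initiation of any glycemic rescue therapy". Section 9.4.1 repeats this for the primary MMRM and for the ≥5% weight-loss analysis: "while on treatment (up to the last dose of study drug plus 7 days) and prior to rescue medication". The protocol's mITT and completers' definitions also carry a rescue condition. Amendment 1 lists no change to Section 9.

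**SAP, primary analysis.** Section 5 gives one cut for the mITT analyses: "Only those measurements taken up to the last dose of study drug plus 14 days will be included in the analysis". Section 5.2.3 gives the same cut for the primary model: "The analysis will use the observed data through Week 12 while on treatment (up to the last dose of study drug plus 14 days"). Section 5.2.2, on the estimand, lists a population, a variable and a summary ("mean percentage change in body weight from baseline to Week 12"), with no entry for rescue. For ≥5% weight loss, 5.3.2 adds: "Subjects without an on treatment weight measurement at Week 12 will be considered non-responders".

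**SAP, secondary analysis.** The ITT analysis is described in 2.2.2 as "including data after initiation of rescue medication and data after the on-treatment period", and in Section 5 as using data "regardless of rescue medication initiation, and regardless of whether on or off-treatment".

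**SAP, elsewhere.** Section 5.4.2 limits glycemic parameters to pre-rescue measurements. The amendment history entry for Section 5 states that all non-glycemic efficacy analyses are done regardless of rescue, with glycemic endpoints kept pre-rescue.

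**The concern.** Rescued subjects continue double-blind drug, so a weight taken after rescue can still be an on-treatment weight, and the question of its inclusion is real. The protocol excludes such weights. The SAP section defining the primary analysis does not say either way, and the only weight analysis for which the SAP text names post-rescue data is the ITT one. Taken together, those ITT sentences suggest that rescue is part of what separates ITT from the primary analysis, as it is in the protocol.

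Two programmers could then build different datasets for the primary and major secondary endpoints. For the responder endpoint the effect is direct: under a pre-rescue cut, a subject rescued before the Week 12 weight has no eligible value and counts as a non-responder, even with a loss of 5% or more.

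**Working it through.** **1. What changed between the documents**

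| Item | Protocol 9.3 / 9.4.1 | SAP |
|---|---|---|
| Primary MMRM data | last dose + 7 days, pre-rescue | last dose + 14 days (5.2.3) |
| ≥5% responder data | last dose + 7 days, pre-rescue | last dose + 14 days (5.3.2) |
| mITT set | needs a pre-rescue weight | no rescue condition (2.2.2) |
| Completers' set | no rescue started | no rescue condition (2.2.2) |
| Glycemic endpoints | modelled like the primary | pre-rescue condition kept (5.4.2) |

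The condition is gone from all four weight-related items and kept only for glycemic parameters. SAP 5.2.3 follows the protocol's wording closely, changes 7 to 14 and omits the rescue clause. That is a consistent edit, and the amendment history describes the same edit.

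**2. Applying the SAP as written.** A rescued subject still on drug with a Week 12 weight has an observed, on-treatment value within last dose + 14 days. Sections 5, 5.2.3 and 5.3.2 all admit it, and no SAP sentence excludes it. The ITT sentences say what that analysis includes; they do not say what the primary leaves out. Reaching exclusion means restoring a clause the SAP deleted.

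**3. Planning figure.** Inputs from SAP 1.4: SD 4, n = 47 per arm, difference 2.7, two-sided 0.05.
- SE = 4 × √(2/47) = 0.825
- Power = Φ(2.7/0.825 − 1.96) = 0.905, matching the stated 90% for one unadjusted comparison.

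**4. Size if the other reading were used.** The documents give no rescue rate, so the counts and gaps below are assumptions.

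*Responder rate.* Each subject rescued before the Week 12 weight, and with ≥5% loss, moves the arm's rate by 1/47 = 2.1 points; three such subjects move it by 3/47 = 6.4 points. A subject whose rescue follows the Week 12 visit is unaffected, because the weight was taken first.

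*Mean change.* Let k be the net number of rescued subjects in one arm and g the gap between the observed Week 12 change and the value the MMRM would imply without it. The shift is k × g / 47.

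| k | g (points) | Shift | Shift / SE | Shift / 2.7 |
|---|---|---|---|---|
| 1 | 1 | 0.02 | 0.03 | 0.8% |
| 1 | 3 | 0.06 | 0.08 | 2.4% |
| 3 | 3 | 0.19 | 0.23 | 7.1% |

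*Precision.* Dropping three Week 12 weights per arm, with nothing recovered from earlier visits, gives SE = 4 × √(2/44) = 0.853, about 3% larger. Losing 5% or 10% of Week 12 weights in both arms gives power of 0.891 or 0.874.

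Rescue is unlikely to be common: Protocol 6.6 requires FPG above 270 mg/dL through Week 6 and above 240 mg/dL afterwards, and post-baseline FPG is scheduled only at Weeks 2, 6 and 12. Home glucose readings can prompt further tests.

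**The case for a change.** The strongest opposing case has four parts.

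- **A change log is not the place for a primary analysis rule.** The rule belongs in 5.2.2 and 5.2.3, with a note that it departs from the protocol. The log gives a reason for moving from 7 to 14 days (pharmacokinetics) but none for rescue. This stands as a drafting criticism. It does not make the rule unknown, because the log and the SAP text agree.
- **Rescue may affect weight and may differ by arm.** Basal insulin is an allowed rescue agent, and exclusion criterion 34 lists insulin among drugs that may change weight. Protocol 2.3 says the drug may raise glucose in some subjects. In the Phase 1 fixed-dose study, mean FPG rose about 19 mg/dL at 10 mg and fell about 33 mg/dL on placebo. This stands as a reason to care which rule applies. It does not favour exclusion: dropping later weights of rescued subjects answers a different question and needs them to be missing at random. SAP 4.2 will report rescued subjects by arm, so an imbalance will be visible.
- **The ITT sentences mislead.** They do suggest that rescue separates the two analyses. Under the SAP's own rules, off-treatment data separate them.
- **Timing.** Protocol 9.4.2 expects a final SAP before randomization, while SAP 3 reports a past DMC review of unblinded safety data. A later SAP amendment is permissible, and nothing shows that its authors saw those data. This part supports no conclusion.

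**Conclusion.** The concern does not call for a change. Read as a whole, the SAP has one rule for weight: on-treatment values up to last dose + 14 days count, whether or not rescue has begun. Keeping rescued subjects' on-treatment weights is a reasonable treatment-policy handling of rescue. The completers' set is also unambiguous, since SAP 2.2.2 defines it by treatment completion alone. Writing the rule into 5.2.3 would help a reader but would alter no dataset and no result. A pre-rescue MMRM would be an additional analysis of a different estimand, not a correction.

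Even under the rejected reading, the illustrative shift in the primary comparison is at most 0.19 points, or 0.23 of a standard error, and each affected responder counts 2.1 points in one arm. These sizes rest on assumed counts of 1 to 3 net rescued subjects and gaps of 1 to 3 points. A higher or strongly unbalanced rescue rate would enlarge them, but it would not change which rule the SAP sets.
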